6.2.1.2 Dosage Adjustments, Delays, Rules for Withholding or Restarting, Permanent Discontinuation

There will be no dose adjustments in this study. If, in the opinion of the investigator, a subject is unable to tolerate a specific dose of investigational product, that subject will discontinue investigational product but will return for all other study procedures and measurements until the end of the study.

If a subject is late for administration of investigational product, administration should occur as soon as possible.

A QM dose of investigational product should not be administered within less than 7 days of a previous dose. If a QM subject arrives for a visit with investigational product administration and investigational product was administered within the prior 7 days, the dose should not be administered but all other study procedures should be conducted. Administration of investigational product should occur as soon as possible but at least 7 days after the previous administration.

Not more than 2 Q2W doses should be administered within any 7-day period. If a Q2W subject arrives for a visit with investigational product administration and more than 1 dose of investigational product was administered within the prior 7 days, the dose should not be administered but all other study procedures should be completed.

Administration of investigational product should occur as soon as possible but at least 7 days after the most recent previous administration.

Subjects who completely miss a dose of investigational product will continue in the study and receive the next dose of investigational product per their schedule of administration.

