9.2.2 Adverse Events

9.2.2.1 Reporting Procedures for Adverse Events That do not Meet Serious Criteria

Adverse events possibly related to study procedures, adverse device effects and serious adverse events are reported from signing of the ICF. All other adverse events are reported from the time of randomization/first dose of investigational product/study treatment/protocol-required therapies. The investigator is responsible for ensuring that all adverse events observed by the investigator or reported by the subject that occur from signing of the ICF or from the time of randomization/first dose of investigational product/study treatment/protocol-required therapies through 30 days after the last administration of investigational product or the EOS visit/safety follow-up visit or whichever is later, are reported using the Event CRF.

Approved

The investigator must assign the following adverse event attributes:

- Adverse event diagnosis or syndrome(s), if known (if not known, signs or symptoms),
- Dates of onset and resolution (if resolved),
- Severity [and/or toxicity per protocol],
- Assessment of relatedness to investigational product (evolocumab/placebo and/or the device (the prefilled Autoinjector/Pen), (AI/Pen) or other protocol-required therapies or study mandated procedures or activity
- Action taken.

The adverse event grading scale used will be the Common Terminology Criteria for Adverse Events (CTCAE). The grading scale used in this study is described in [Appendix A](#).

The investigator must assess whether the adverse event is possibly related to investigational medicinal product (IMP) (evolocumab or placebo). This relationship is indicated by a “yes” or “no” response to the question: Is there a reasonable possibility that the event may have been caused by evolocumab or placebo (investigational medicinal product)?

The investigator must assess whether the adverse event is possibly related to the prefilled Autoinjector/Pen investigational device used to administer evolocumab or placebo. The relationship is indicated by a “yes” or “no” response to the question: Is there a reasonable possibility that the event may have been caused by the investigational device?

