9.2.2.2 Reporting Procedures for Serious Adverse Events

The investigator is responsible for ensuring that all serious adverse events observed by the investigator or reported by the subject that occur after signing of the ICF through 30 days after the last administration of investigational product or the EOS/ safety follow-up visit, whichever is later, are recorded in the subject's medical record and are submitted to Amgen. This study will be utilizing electronic data capture for serious adverse events. All serious adverse events must be submitted to Amgen within 24 hours following the investigator's knowledge of the event via the Event CRF.

If the electronic data capture (EDC) system is unavailable to the site staff to report the serious adverse event, the information is to be reported to Amgen via an electronic serious adverse event Contingency Report Form within 24 hours of the investigator's knowledge of the event. See [Appendix B](#) for a sample of the electronic Serious Adverse Event Contingency Report Form. For EDC studies where the first notification of a serious adverse event is reported to Amgen via the eSerious Adverse Event Contingency Report Form, the data must be entered into the EDC system when the system is again available.

The investigator must assess whether the serious adverse event is possibly related to investigational medicinal product (IMP) (evolocumab or placebo). This relationship is indicated by a "yes" or "no" response to the question: Is there a reasonable possibility that the event may have been caused by evolocumab or placebo (investigational medicinal product)?

The investigator must assess whether the serious adverse event is possibly related to the prefilled Autoinjector/Pen investigational device used to administer evolocumab or placebo. The relationship is indicated by a "yes" or "no" response to the question: Is there a reasonable possibility that the event may have been caused by the investigational device?

Approved

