10.5.4 Safety Endpoints

10.5.4.1 Treatment Emergent Adverse Events

The current Medical Dictionary for Regulatory Activities (MedDRA) version at the time of the data lock will be used to code all adverse events to a system organ class and a preferred term.

Subject incidence of all treatment emergent adverse events will be tabulated by system organ class and preferred term. Tables of fatal adverse events, serious adverse events, adverse events leading to withdrawal from investigational product, device-related adverse events, and significant treatment-emergent adverse events will also be provided. Subject incidence of disease-related events and fatal disease-related events will be tabulated by system organ class and preferred term.

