### Treatment Emergent Adverse Event (TEAE)

Events categorized as Adverse Events (AEs) starting on or after first dose of investigational product as determined by **“Did event start before first dose of**

“investigational product” equal to “No” or missing on the Events eCRF, and up to 30 days after the last dose of investigational product or EOS date, whichever is earlier.

Treatment Emergent Serious Adverse Event (TESAE)

Treatment-emergent adverse events (as defined above) that are indicated as serious on the Events eCRF.

Reflexive Approach for LDL-C and VLDL-C

For all analyses related to LDL-C and VLDL-C, unless specified otherwise, the following reflexive approach will be used. When calculated LDL-C is less than 40 mg/dL or triglycerides > 400 mg/dL, the UC LDL-C value from the same blood sample will be used instead of calculated LDL-C and the UC VLDL-C value from the same blood sample will be used instead of calculated VLDL-C, if available.

Achievement of LDL-C < 70 mg/dL

A subject has achievement of LDL-C < 70 mg/dL if the post-baseline LDL-C value is less than 70 mg/dL. If the value is missing, the subject is considered without the achievement.

Mean achievement of LDL-C < 70 mg/dL at weeks 10 and 12 is defined using the mean of non-missing LDL-C values at those two timepoints (if one is missing, mean equals the available one). If both the values at weeks 10 and 12 are missing, the subject is considered without the achievement.

LDL-C response (50% reduction from baseline)

A subject has a response of 50% reduction from baseline in LDL-C, if the LDL-C percent change from baseline value is less than or equal to -50%. If the value is missing, the subject is considered without the response when statistical inference is performed.

Mean response of LDL-C 50% reduction at weeks 10 and 12 is defined using the mean of non-missing LDL-C percent change from baseline values at those two timepoints (if one is missing, mean equals the available one). If both the values at weeks 10 and 12 are missing, the subject is considered without the response when statistical inference is performed.

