### 9.5.1 Analyses of Primary Efficacy Endpoint(s)

To assess the co-primary endpoints as described in the co-primary estimands a repeated measures linear effects model including all observed values (on and off treatment) will be used on the FAS in each dose frequency to compare the efficacy of evolocumab with placebo. The repeated measures model will include terms for treatment group, stratification factor, scheduled visit and the interaction of treatment with scheduled visit. Missing values will not be imputed for primary analysis.

To account for the repeated LDL-C measurements within a subject across the visits, the repeated measures linear effects model will use an unstructured covariance.

Multiplicity adjustment procedures are defined in [Section 9.1](#).

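### SAP 5.3 closes the adverse-event window at the earlier of last dose + 30 days or EOS, the protocol collects to the later, and no table is planned for serious, fatal and disease-related events in between

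*SAP*

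**What the plan says.** **Analysis window.** SAP 5.3 counts adverse events that start on or after the first dose and "up to 30 days after the last dose of investigational product or EOS date, whichever is earlier". Serious treatment-emergent events are defined as "Treatment-emergent adverse events (as defined above) that are indicated as serious on the Events eCRF", so they inherit the same end date.

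**Collection period.** Protocol 9.2.2.1 requires adverse events to be reported "through 30 days after the last administration of investigational product or the EOS visit/safety follow-up visit or whichever is later". Protocol 9.2.2.2 requires serious adverse events to be reported "through 30 days after the last administration of investigational product or the EOS/ safety follow-up visit, whichever is later". Protocol 9.2.1 uses the same later-of-two rule for disease-related events.

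**Follow-up after stopping product.** Under Protocol 6.2.1.2, if a dose is not tolerated, "that subject will discontinue investigational product but will return for all other study procedures and measurements until the end of the study". Protocol 3.1 adds that all subjects are to be urged to attend every visit, whether or not they adhere to product.

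**Tables.** Protocol 10.5.4.1 plans "Tables of fatal adverse events, serious adverse events, adverse events leading to withdrawal from investigational product", among others, and gives no end date for events to be included. SAP 9.6.1 tabulates treatment-emergent, serious and fatal events, adds disease-related events to those summaries and also tabulates them separately, and refers to 5.3 for the meaning of treatment-emergent. It plans no table or listing of events that start after the window. SAP 10, on changes from the protocol, does not mention the window.

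**The concern.** The two documents use the same two dates and take opposite ends. An event between those dates is recorded on the Event CRF but has no place in the adverse-event tables. For most subjects the interval is negligible. It becomes long for subjects who stop product early and stay in the study, as the protocol asks of them. These subjects remain in the safety denominator in full, because SAP 6.2 makes the Safety Analysis Set the same as the FAS.

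What is at stake is completeness. A new serious or disease-related event more than 30 days after an early last dose would be collected and then not shown in any event table. A late death would be counted by arm as a reason for leaving the study, with no event term and no entry in the fatal-event table.

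**Working it through.** The plan states no figure to reproduce; this is a date rule, so the check is day arithmetic.

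**Inputs**
- Study day for week w is 7 × w + 1 (SAP Appendix F).
- EOS day E: QM at Week 12, Day 85; Q2W at Week 14, 7 × 14 + 1 = Day 99 (Protocol 3.1).
- Planned dose days (Protocol Table 2 and its footnotes): QM 1, 29, 57; Q2W 1, 15, 29, 43, 57, 71.

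**Formulas**, with L the day of the last dose
- SAP cut-off = min(L + 30, E)
- Protocol collection end = max(L + 30, E)
- Gap = collection end − cut-off

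**Subjects who stop before the last planned dose and stay to scheduled EOS**

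| Regimen | Last dose day | SAP cut-off | Collection end | Gap (days) | Gap ÷ collection end |
|---|---|---|---|---|---|
| QM | 1 | 31 | 85 | 54 | 64% |
| QM | 29 | 59 | 85 | 26 | 31% |
| Q2W | 1 | 31 | 99 | 68 | 69% |
| Q2W | 15 | 45 | 99 | 54 | 55% |
| Q2W | 29 | 59 | 99 | 40 | 40% |
| Q2W | 43 | 73 | 99 | 26 | 26% |
| Q2W | 57 | 87 | 99 | 12 | 12% |

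An EOS at the end of the +3 day window adds 3 days to each gap.

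**Subjects who take every dose.** Protocol 3.1 requires EOS at least 30 days after the last dose. Among combinations of ±3 days on last dose and EOS that meet this, the smallest gap is 0. The largest has the dose 3 days early and EOS 3 days late: QM (85 + 3) − (57 − 3) − 30 = 4; Q2W (99 + 3) − (71 − 3) − 30 = 4. The range is 0 to 4 days.

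On nominal days, EOS is only 28 days after the last dose in both regimens (85 − 57 and 99 − 71), which does not meet the 30-day requirement. Those passages need to be reconciled separately. The nominal gap is then 30 − 28 = 2 days.

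**Subjects who leave the study early.** If EOS falls before L + 30, the SAP stops at EOS while the protocol's rule runs on. With EOS 10 days after the last dose, for example, the difference is 30 − 10 = 20 days.

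**After the fix.** A table that runs to max(L + 30, E) has a gap of 0 days for every subject.

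**The case against.** The strongest reply is that a collection period is not an analysis period. The protocol's safety endpoint is the incidence of treatment-emergent events, it sets no end date for that term, and the SAP may fill it in with 30 days after the last dose. That stands: the on-treatment window is not an error. What it leaves open is where the remaining collected serious, fatal and disease-related events are shown.

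Second, SAP 9.6.1 can be read more broadly. In its list of tables the treatment-emergent qualifier is attached to the first item only, its restatement of the term gives no end date, and the window in 5.3 is written for adverse events and not expressly for disease-related events. This is a genuine ambiguity. The reference back to 5.3 and the explicit definition of serious treatment-emergent events favour the restricted reading. If the broad reading is meant, the SAP should say so.

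Third, the cut-off applies to onset. An event that starts inside the window and later proves serious or fatal is counted, and the event that led to stopping would ordinarily fall inside it. That also stands; the gap concerns new events that start after the window.

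A reader might go further than the documents allow in four ways:
- *That deaths could vanish from the report.* Death is a listed reason for removal from study (Protocol 8.3.2), and SAP 9.2 summarizes reasons for discontinuing the study by treatment group.
- *That only early stoppers are affected.* Subjects who take every dose can lose up to 4 days, and early leavers lose days within the protocol's collection rule.
- *That the 10% dropout figure in the sample-size section gives the number affected.* It is a power assumption. It is not a rate of stopping product while staying in follow-up.
- *That the use of off-treatment values in the efficacy model shows the safety window to be inconsistent.* The primary estimand applies regardless of product discontinuation; treatment-emergent safety asks a different question.

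**Conclusion.** The mismatch is real, and its consequence is limited but specific. On the restricted reading of SAP 9.6.1, collected serious adverse events, fatal events and disease-related events with onset after the window are missing from the event tables, and nothing else in the plan tabulates them as events. For a subject who stays to scheduled EOS the gap is at most 54 days (QM) or 68 days (Q2W).

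These figures assume dosing and EOS on scheduled days. The documents give no rate of stopping product with continued follow-up, so neither the number of subjects nor the number of events can be derived. Nor do they give grounds for assuming that stopping differs between arms, so a differential bias is possible but not shown. The change is worth making because it is cheap and uses data already collected; the on-treatment analysis is not invalid without it.

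**What to change.** Keep the window in SAP 5.3 for the treatment-emergent tables. Add to SAP 9.6.1 tables of serious adverse events, fatal events and disease-related events from first dose through the end of protocol collection, that is, the later of EOS or last dose + 30 days, by actual treatment group. State in the same section that the existing serious, fatal and disease-related tables use the 5.3 window, so that the two sets can be told apart.

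Changing the earlier-of rule in 5.3 to a later-of rule is not recommended. It would label events long after the last dose as treatment-emergent, which is a debatable trade-off and is not needed to close the gap.

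The cost is a short SAP edit and a few extra tables, with no new data collection. The downside is that some off-drug events are displayed.

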4.1 Inclusion and Exclusion Criteria

4.1.1 Inclusion Criteria

- 101 Male or female \geq 18 years of age at signing of informed consent form
- 102 On an approved statin, with or without ezetimibe, at optimal stable daily dose(s) for at least 4 weeks before LDL-C screening and, in the opinion of the investigator, not requiring uptitration
- 103 Fasting LDL-C as determined by central laboratory at screening \geq 80 mg/dL
- 104 Subject meets at least one of the following criteria for high/very high CV risk :
 - history of coronary artery disease
 - history of ischemic stroke
 - diagnosis of peripheral artery disease
 - an estimated glomerular filtration rate (eGFR) as determined by central laboratory at screening of \geq 30 but $<$ 60 ml/min/1.73m²
 - diagnosis of diabetes mellitus type 2
 - presence of \geq 3 of the following risk factors:
 - \geq 45 years of age if male, \geq 55 years of age if female
 - hypertension
 - smoking
 - family history of premature CVD (1st degree of relative: male $<$ 55yr, female $<$ 65yr)

- HDL cholesterol < 40 mg/dL
- obesity(BMI \geq 28 kg/m²)

OR

Subject does not meet high/very high CV risk criteria but fasting LDL-C as determined by central laboratory at screening \geq 130 mg/dl

105 Fasting triglycerides \leq 400 mg/dL (4.5 mmol/L) by determined by central laboratory at screening

106 Subject tolerates a screening placebo injection

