### **3.2            Sample Size**

The sample size for this study has been considered to meet the requirement from regulatory authority (Drug Registration Regulation No 28; Oct 2007).

The planned total sample size is 450 subjects (150 randomized to evolocumab SC 140 mg Q2W, 150 randomized to evolocumab SC 420 mg QM, 75 randomized to placebo Q2W and 75 randomized to placebo QM). The primary analysis will require the tests of each co-primary endpoint to be significant at level of 0.05. The sample size should provide adequate power to determine the superiority of evolocumab (either Q2W or QM) relative to respective placebo (Q2W or QM) as measured by the co-primary endpoints.

From the phase 3 study 20120122 and phase 2 study 20110155, the mean treatment effect of evolocumab 140 mg Q2W and 420 mg QM compared to placebo in percent

change from baseline in LDL-C at week 12 was at least -50.3%, with the smallest treatment effect of -44.6% estimated from 95% confidence intervals. For the co-primary endpoint of mean percent change from baseline in LDL-C at weeks 10 and 12, the mean treatment effect of evolocumab 140 mg Q2W and 420 mg QM compared to placebo was at least -62.4%, with the smallest treatment effect of -57.2% estimated from 95% confidence intervals.

The assumed treatment effect of evolocumab in LDL-C reduction is 40%, with a common SD of 25%. As the co-primary endpoints are correlated, the planned sample size will provide approximately at least 98% (99% x 99%) power in testing the superiority of each evolocumab dosing regimen over placebo on the co-primary endpoints, assuming a 10% drop out rate.

Since the testing statistics from Q2W and QM groups are independent, there is a 96% chance (98% x 98%) to show the superiority of both evolocumab dosing regimens over placebo.

The power calculation is derived using SAS Enterprise Guide version 6.1.

**Seventeen subjects who were enrolled in the study will be excluded from all analyses (both efficacy and safety) because they would require additional Human Genetic Resource Administration office of China (HGRAC) approvals, as follows:**

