#### Baseline lipid and lipid related parameters

Baseline values for lipids (total cholesterol, HDL-C, **non-HDL-C**, LDL-C, VLDL-C and triglycerides), ApoA1, ApoB, Lp(a) and their derived parameters (eg, ratio between them) are defined as the mean of the two most recent non-missing concentrations measured through central lab prior to or on Study Day 1. If for any reason only 1 value is available, then that value will be used as baseline.

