#### **8.4 Detection of Bias**

This study has been designed to minimize potential bias by the use of randomization of subjects into treatment groups and the use of blinding. Other factors that may bias the results of the study include:

- Major protocol deviations likely to impact the analysis and interpretation of the efficacy endpoints.
- Subject level unblinding before final database lock and formal unblinding.

Important protocol deviations likely to impact the analysis and interpretation of the efficacy endpoints will be tabulated in the Clinical Study Report (CSR).

Any unblinding of individual subjects prior to formal unblinding of the study will be documented in the CSR. The impact of such unblinding on the results observed will be assessed. Data from subjects whose treatment assignments are unblinded prior to formal unblinding will be listed. The timing and reason for unblinding will be included in these listings.

Additional sensitivity and/or supplementary analyses may be included to assess the impact of potential biases on the co-primary endpoints. If any sensitivity analyses are required to evaluate potential biases in the study's conclusions, then the sources of the potential biases and results of the sensitivity and/or supplementary analyses will be documented in the CSR.

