**Table 9-2. Secondary Efficacy Endpoint Summary Table**

Endpoint	Primary Summary and Analysis Method (Specify Analysis Set if FAS is Not Used)	Sensitivity Analysis

Mean LDL-C achievement of target LDL-C < 70 mg/dL and LDL-C response of <math>\geq 50\%</math> reduction from baseline at weeks 10 and 12

LDL-C achievement and response at week 12

	Cochran Mantel-Haenszel (CMH) test	N/A
Mean percent change from baseline at weeks 10 and 12 Percent change from baseline at week 12 in each of the following lipid parameters: Lp(a), triglycerides, HDL-C and VLDL-C	Repeated measures model assuming MAR including all observed values (on and off IP)	N/A

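### Does switching VLDL-C to ultracentrifuged values at low LDL-C, mostly on evolocumab, bias the tier 2 VLDL-C comparison or leave a gap in the plan?

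*SAP*

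**What the plan says.** SAP 5.3 sets the rule under its reflexive-approach definition: "For all analyses related to LDL-C and VLDL-C, unless specified otherwise, the following reflexive approach will be used". The trigger reads "When calculated LDL-C is less than 40 mg/dL or triglycerides > 400 mg/dL". LDL-C and VLDL-C are then both taken from ultracentrifugation (UC) of that sample; for VLDL-C, "the UC VLDL-C value from the same blood sample will be used instead of calculated VLDL-C, if available". Nothing elsewhere in the SAP makes an exception for VLDL-C.

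Baseline (SAP 5.2) is "defined as the mean of the two most recent non-missing concentrations measured through central lab prior to or on Study Day 1". Protocol 4.1.1 requires "Fasting LDL-C as determined by central laboratory at screening" to be at least 80 mg/dL, or at least 130 mg/dL for subjects not at high or very high cardiovascular risk, and triglycerides to be at most 400 mg/dL.

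VLDL-C percent change is one of four tier 2 endpoints, tested by Hochberg (SAP 9.1). Its Table 9-2 entry, "Percent change from baseline at week 12 in each of the following lipid parameters: Lp(a), triglycerides, HDL-C and VLDL-C", has a repeated measures model as the main analysis and not applicable under sensitivity analysis. The other row of that table, for the LDL-C target and response endpoints, says the same. SAP 8.4 allows further work on bias, but for the primary comparison: "Additional sensitivity and/or supplementary analyses may be included to assess the impact of potential biases on the co-primary endpoints".

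**The concern.** The entry limits mean that baseline VLDL-C is nearly always a calculated value. After baseline, a sample changes method when LDL-C drops below 40 mg/dL, and the drug is what makes it drop. Randomisation cannot balance something that treatment causes. If UC and calculated VLDL-C differ on average in those samples, part of the difference between arms could be a difference between assays and not a difference in VLDL-C. The words allowing for an unavailable UC result could also mix the two methods within the evolocumab arm.

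VLDL-C is tested under familywise control, so a false rejection would count as a formal claim. With no sensitivity analysis and no planned count of switched samples, the report would not show how far the result depends on the switch.

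**Working it through.** **Inputs.** From SAP 3.2: "The assumed treatment effect of evolocumab in LDL-C reduction is 40%, with a common SD of 25" per cent; prior effects of -50.3% (week 12) and -62.4% (mean of weeks 10 and 12); 150 evolocumab and 75 placebo subjects per dose frequency; 10% dropout, giving 135 and 67.5. Assumed, because the documents do not give them: baseline LDL-C of 80 to 160 mg/dL, normality, zero mean change on placebo, VLDL-C SD of 40%, and an average method difference d = UC minus calculated, in points of baseline VLDL-C.

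**The plan's own figure.** It states no VLDL-C quantity. The only related figure is the co-primary power of at least 98%. With SE = 25 × √(1/135 + 1/67.5) = 3.73, the 40% effect is 40/3.73 = 10.7 standard errors. Power exceeds 99.9%, consistent with the stated floor, and the VLDL-C question does not touch it.

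**Step 1: how uneven is the switch?** The share below 40 mg/dL is Φ((effect size − required fall)/25), with required fall = 100 × (1 − 40/baseline). At baseline 130 the required fall is 69.2%, so evolocumab at 40% gives Φ(−1.17) = 12.1% and placebo gives Φ(−2.77) = 0.3%.

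| Baseline (mg/dL) | Placebo | Evolocumab, 40% | 50.3% | 62.4% |
|---|---|---|---|---|
| 80 | 2.3% | 34.5% | 50.5% | 69.0% |
| 100 | 0.8% | 21.2% | 34.9% | 53.8% |
| 130 | 0.3% | 12.1% | 22.4% | 39.2% |
| 160 | 0.1% | 8.1% | 16.2% | 30.7% |

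The switch is therefore heavily one-sided. These shares are upper bounds for the LDL-C trigger, because a UC result must also exist.

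**Step 2: what would it do if the calculated value were right?** Shift under a true null = (evolocumab share − placebo share) × d. SE = 40 × √(1/135 + 1/67.5) = 5.96. For d = 10 at the 40% effect, the shift is 0.118 × 10 = 1.18 points at baseline 130 and 0.322 × 10 = 3.22 points at baseline 80. Rejection rates of a single two-sided 0.05 test with d = 10:

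| Baseline (mg/dL) | 40% | 50.3% | 62.4% |
|---|---|---|---|
| 80 | 8.4% | 12.8% | 20.1% |
| 100 | 6.3% | 8.8% | 14.4% |
| 130 | 5.5% | 6.6% | 10.0% |
| 160 | 5.2% | 5.8% | 8.1% |

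With d = 5 at the 40% effect the range is 5.1% (baseline 130) to 5.8% (baseline 80). A shift of 3.89 points gives 10% rejection, so at the 40% effect d must reach 3.89/0.118 = 33 points at baseline 130, or 3.89/0.322 = 12 at baseline 80. Baseline 80 puts the average subject at the entry minimum, so that row is a limiting case.

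The planned test is also stricter than a single 0.05 test. Under Hochberg, 0.05 applies to VLDL-C only if the other three tier 2 p-values are at most 0.05. At the strictest step, 0.05/4 = 0.0125, d = 10 at the 40% effect and baseline 130 gives 1.4%. If the union-intersection test of Protocol 10.5.3 is a Bonferroni pair (its form is not stated), simulation with a week 10/12 correlation of 0.5 to 0.9 gives 3.4% to 4.2% for that case and 5.7% to 7.3% at baseline 80, against 3.1% to 3.8% with no method difference.

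**Step 3: whose error is it?** Step 2 charges all of d to the planned analysis. Write T for the true VLDL-C in a switched sample. The planned analysis has error UC − T there; a calculated-only analysis has error calculated − T. The data show only the difference of the two, d. For d = 10, baseline 130 and the 40% effect:

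| Which value equals T in switched samples | Error, planned analysis | Error, calculated-only |
|---|---|---|
| Calculated | +1.18 | 0 |
| UC | 0 | −1.18 |

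Both rows produce the same recorded values, the same switch counts and the same paired differences. In the second row the 5.5% rejection rate belongs to the calculated-only repeat, and the planned analysis keeps its 5%. The SAP prefers UC at low LDL-C or high triglycerides, which suggests that its authors regard the calculated value as less dependable there. If the calculated value is sound outside that range and UC is sound within it, switching is what keeps baseline and follow-up comparable.

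**The case for a change.** The strongest argument for acting is that treatment decides which method supplies the endpoint, that the size of the method difference could be read from the trial's own paired samples, and that a table of switch counts and paired differences would cost almost nothing. At the larger prior effects the unfavourable reading is not trivial: with 10 points, 12.8% at baseline 80 for -50.3%, and 10.0% at baseline 130 for -62.4%. An average difference near zero would also reassure a reader.

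Much of this stands as fact. The switch is one-sided, it is not examined, and counts by arm would make the report more transparent. What does not follow is that the planned analysis is biased or incomplete. The method difference and the VLDL-C SD are both assumed. A repeat on calculated values may itself be less accurate at low LDL-C, again mostly on evolocumab, and loses any sample without a calculated value. If the two analyses disagreed, nothing in the documents would say which to believe. The rule itself is prespecified, depends on the sample and not on the arm label, and follows the SAP's general pattern of listing sensitivity analyses for the co-primary endpoints and none in Table 9-2.

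**Conclusion.** The concern does not hold. The uneven switching is real: 8% to 34% of evolocumab samples at the plan's 40% effect, against 0.1% to 2.3% on placebo, over assumed baselines of 160 down to 80 mg/dL. Unequal use of a more suitable measurement is not a bias in itself. Harm needs an average method difference, which the documents neither state nor imply, and needs the calculated value to be the correct one in switched samples. On that reading, with an assumed 10-point difference and VLDL-C SD of 40%, a single 5% test at the 40% effect rejects 5.2% to 8.4% of the time over the same baselines; the inflation is larger at the prior-study effects. If UC is correct in those samples, the planned analysis has no inflation at all.

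A calculated-only repeat would leave the main analysis, the alpha scheme and every tested result as they are, and could not tell the two readings apart. Reporting switch counts would be a matter of reporting preference; its absence is not an error. Co-primary and tier 1 conclusions do not depend on VLDL-C.
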